11.0 STATISTICAL AND ETHICAL CONSIDERATIONS

11.1 Sample Size and Study Duration

The study will be completed in 2 parts. Part A will be a dose-escalation phase including patients with non-CNS solid tumors, and Part B will include a safety and imaging evaluation in patients with CNS tumors.

THIS PROTOCOL IS FOR RESEARCH PURPOSES ONLY, SEE PAGE 1 FOR USAGE POLICY

A minimum of 2 evaluable patients will be entered at each dose level for determination of MTD. Once the MTD or recommended Phase 2 dose has been defined, up to 6 additional patients with recurrent or refractory solid tumors without restrictions on hematologic evaluable may be enrolled to acquire PK data in a representative number of young patients (e.g. six patients < 12 years old and six patients \geq 12 years old). Review of the enrollment rate into previous COG new agent studies indicates that 1-2 patients per month are available. The anticipated maximum number of evaluable subjects required to complete Part A is 24 patients. Assuming a 20% inevaluable rate, 29 patients may be enrolled and the study would be expected to be completed within 15-29 months. A maximum of 51 patients may be required in the unlikely event that each of the three dose levels are expanded to 12 because two DLTs of different types are observed at each of the three dose levels, 6 additional patients are needed for PK analysis, and a 20% inevaluable rate. The maximum of 51 would be completed within 26-51 months.

Part B of the study will require up to 6 evaluable patients enrolled at the MTD or RP2D as determined in Part A. Allowing for 20% inevaluability, 8 patients may be enrolled, and this would be expected to be completed within 4-8 months. If Part B is expanded to 12 because of two different classes of DLTs, then up to 15 patients could be enrolled. The maximum of 15 patients is expected to be completed within 8-15 months.

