5.0 TREATMENT PROGRAM

5.1 Overview of Treatment Plan

Treatment Schedule Table		
Day	Ramucirumab (i.v. over 60 minutes)	Disease Evaluation
1	X	
15	X	

THIS PROTOCOL IS FOR RESEARCH PURPOSES ONLY, SEE PAGE 1 FOR USAGE POLICY

29	X	
42		X

A cycle of therapy is considered to be 42 days. A cycle may be repeated for a total of 8 cycles, up to a total duration of therapy of approximately 12 months. This is an open-label study.

Effort should be made to begin protocol therapy on Monday through Thursday if possible to accommodate correlative sample shipments.

Drug doses should be adjusted based on actual weight measured within 7 days prior to the beginning of each cycle.

Update: With the release of Amendment #2A, the dose escalation portion of the study is complete. Given this, Part B will open to patients with relapsed or refractory CNS tumors.

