11.2.2 Maximum Tolerated Dose

- The MTD will be the maximum dose at which fewer than one-third of patients experience DLT (See [Section 5.5](#)) during Cycle 1 of therapy.
- In the event that two DLTs observed out of 6 evaluable patients are different classes of Adverse Effects (e.g. hepatotoxicity and myelosuppression), expansion of the cohort to 12 patients will be considered if all of the following conditions are met:
 - One of the DLTs does not appear to be dose-related
 - The Adverse Effects are readily reversible
 - The study chair, DVL statistician, DVL committee chair or vice chair, and IND sponsor all agree that expansion of the cohort is acceptable

If fewer than 1/3 of patients in the expanded cohort experience dose-limiting toxicities, the dose escalation can proceed.

THIS PROTOCOL IS FOR RESEARCH PURPOSES ONLY, SEE PAGE 1 FOR USAGE POLICY

- The DLTs observed in the pharmacokinetic (PK) expansion cohort will be counted towards the total number of DLTs observed at the MTD during the dose escalation portion of the study. If $\geq 1/3$ of the cohort of patients at the MTD (during the dose escalation plus the PK expansion) experience DLT then the MTD will be exceeded.

11.2.3 Recommended Phase 2 Dose (RP2D):

After accrual to dose level 2 is completed, PK comparisons from dose levels 1 and 2 will be performed. An expansion cohort will accrue at the lowest tolerable dose at which C_{min} of ≥ 50 μ g/mL has been achieved in at least 5 out of 6 evaluable patients to acquire PK data in a representative number of young patients (i.e. patients < 12 years old). If at least 10 out of the total 12 evaluable patients have a steady state concentration of ramucirumab greater than 50 μ g/mL, then the RP2D has been defined. If $C_{min,ss}$ of ≥ 50 μ g/mL has not been achieved in at least 5 out of 6 evaluable patients from dose level 2, and if the MTD has not yet been reached, then dose level 3 will be considered.

11.3 **Dose Escalation and Determination of MTD**

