#### Part A:

A minimum of 2 evaluable patients will be entered at each dose level for determination of MTD. Once the MTD or RP2D has been defined, up to 6 additional patients with recurrent or refractory solid tumors without restrictions on hematologic evaluability may be enrolled to acquire PK data in a representative number of young patients. The anticipated maximum number of evaluable subjects required to complete Part A is 24 patients. Assuming a 20% inevaluable rate, 29 patients may be enrolled.

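### Are the Part A enrolment figures of 29 and 51 too low for the stated 20% inevaluable rate?

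*Protocol*

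**What the plan says.** Protocol section 11.1 puts the anticipated maximum for Part A at 24 evaluable patients and continues: "Assuming a 20% inevaluable rate, 29 patients may be enrolled and the study would be expected to be completed within 15-29 months". SAP section 5.2 repeats the planning figure: "Assuming a 20% inevaluable rate, 29 patients may be enrolled".

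For the extreme case the protocol says: "A maximum of 51 patients may be required in the unlikely event that each of the three dose levels are expanded to 12". That case also includes six further patients for PK and the same 20% rate, and its duration is given as: "The maximum of 51 would be completed within 26-51 months". The SAP does not repeat 51.

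For Part B, which needs up to six evaluable patients, the same protocol section says: "Allowing for 20% inevaluability, 8 patients may be enrolled". If Part B is expanded to 12, up to 15 may be enrolled.

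Three other places bear on the point:

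- Protocol section 11.2.1 replaces patients who are not evaluable for toxicity.
- Section 11.2.3 counts evaluable patients at the expanded dose when it defines the RP2D: "If at least 10 out of the total 12 evaluable patients have a steady state concentration of ramucirumab" above the target, the RP2D is defined.
- Section 11.2.2 pools toxicity across the escalation and the expansion: "The DLTs observed in the pharmacokinetic (PK) expansion cohort will be counted towards the total number of DLTs observed at the MTD".

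**The concern.** An inevaluable rate is most naturally read as a share of the patients enrolled. To end with n evaluable patients at a 20% loss, one divides n by 0.8. Multiplying n by 1.2 is a common slip and gives too few. Both Part A figures equal n × 1.2 rounded up, so they look like that slip.

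If so, planned enrolment, the stated maximum and both durations are slightly low for the rate printed beside them. The reader also cannot tell whether the six PK expansion patients carry any allowance. That could matter because the RP2D rule in section 11.2.3 is framed on 12 evaluable patients, six of whom would come from the expansion in the base case.

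**Working it through.** **Inputs (Protocol section 11.1).** 24 evaluable in the base case, which matches 3 dose levels × 6 + 6 PK patients. In the expanded case, 3 × 12 + 6 = 42 evaluable; this sum is derived, not printed. The inevaluable rate is 20% and accrual is 1–2 patients per month.

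**Reproducing the printed figures.** The protocol states no formula. Two routes return both numbers.

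| Route | Base case | Expanded case |
|---|---|---|
| (a) n × 1.2, rounded up | 24 × 1.2 = 28.8 → 29 | 42 × 1.2 = 50.4 → 51 |
| (b) dose-level patients ÷ 0.8, plus 6 PK patients | 18/0.8 + 6 = 28.5 → 29 | 36/0.8 + 6 = 51 |
| All patients ÷ 0.8, rounded up | 24/0.8 = 30 | 42/0.8 = 52.5 → 53 |

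Route (b) applies the correct division to the dose-level patients. It also fits the description of the PK group in section 11.1 as up to six more patients who may be enrolled. Against it, the same section calls all 24 evaluable.

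**Size of the gap if 20% of all enrolled patients are inevaluable.**

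- Base case: 29 × 0.8 = 23.2 expected evaluable, 0.8 below 24. The rate that 29 absorbs is 5/29 = 17.2%.
- Expanded case: 51 × 0.8 = 40.8, 1.2 below 42. The rate that 51 absorbs is 9/51 = 17.6%.
- Durations: 30 patients would take 15–30 months (printed 15–29). 53 would take 27–53 months, since 53/2 = 26.5 (printed 26–51).

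**Comparison with chance.** With a binomial count at 80% evaluable, the standard deviation is √(29 × 0.8 × 0.2) = 2.2 for 29 patients and √(51 × 0.8 × 0.2) = 2.9 for 51. The shortfalls are about 0.4 SD each. The chance of at least 24 evaluable is 0.46 with 29 enrolled and 0.61 with 30. The chance of at least 42 is 0.42 with 51 and 0.63 with 53. The larger figures do not secure the targets either.

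**Does Part B show which formula was used?** No. 6/0.8 = 7.5 and 6 × 1.2 = 7.2 both round up to 8. 12/0.8 = 15 and 12 × 1.2 = 14.4 → 15 agree as well.

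**Does the 12-evaluable RP2D rule rule out route (b)?**

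- In the expanded case it does not. Each dose level already has 12 evaluable patients before the PK patients are added.
- In the base case there is some tension: six enrolled PK patients give 6 × 0.8 = 4.8 evaluable in expectation.
- Counting expansion DLTs towards the MTD needs no allowance, because under section 11.2.1 a dosed patient who has a DLT is evaluable.
- The evaluability defined in section 11.2.1 concerns toxicity, whereas the 10-of-12 rule concerns trough concentrations, and section 11.6.3 defines a separate PK set. A single 20% rate need not apply to both.

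**The case for a change.** The strongest case for a change is that 29 stands in both documents beside a rate that it does not cover on the ordinary reading. Multiplying by 1.2 allows for only 0.2/1.2 = 16.7% of those enrolled before rounding. Route (b) leaves the PK expansion without an allowance, although in the base case the RP2D rule looks for 12 evaluable patients. Since two formulas fit and neither is stated, anyone comparing planned with actual inevaluability starts from an unclear figure, and one sentence would settle it.

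The arithmetic stands, and so does the remark that the formula is missing. The tension with the RP2D rule stands for the base case only. What does not stand is the step from there to a defect in the plan. The printed figures are reproducible, Part B offers no evidence of inconsistency, and the difference is well inside the chance variation of the evaluable count.

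**Conclusion.** No change follows, because nothing would be gained. On the reading least favourable to the plan, the difference is one enrolled patient in the base case (30 against 29) and two in the expanded case (53 against 51), or 0.8 and 1.2 expected evaluable patients. This rests on taking 20% as a share of all enrolled patients and on the derived total of 42.

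The consequences are nil for three reasons:

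- The targets are reached by replacement (Protocol sections 11.2.1 and 11.3), not by fixing enrolment in advance. The 24 is an anticipated maximum and the 29 is worded as permission.
- The trial has no hypothesis test whose power could fall, and no escalation rule, RP2D criterion or analysis refers to 29 or 51.
- Section 5.1 records: "With the release of Amendment #2A, the dose escalation portion of the study is complete". Section 5.3 gives the RP2D as 12 mg/kg, so the scenario behind 51 is now hypothetical.

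An author revising the text for other reasons could state the inflation formula and whether the six PK patients are inflated. That would be a courtesy to the reader and would not alter conduct, analysis or conclusions.

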11.2 Definitions

11.2.1 Evaluable For Adverse Effects

Any patient who receives at least one dose of the study drug(s) and who experiences a dose-limiting toxicity is considered evaluable for Adverse Events. In addition, during Cycle 1, patients must have the appropriate toxicity monitoring studies performed to be considered evaluable for dose limiting toxicity. Patients who do not have DLT and do not receive at least 85% of the prescribed dose within the first cycle for reasons other than toxicities (e.g. progressive disease) will not be considered evaluable for toxicity and will be replaced.

11.2.2 Maximum Tolerated Dose

- The MTD will be the maximum dose at which fewer than one-third of patients experience DLT (See [Section 5.5](#)) during Cycle 1 of therapy.
- In the event that two DLTs observed out of 6 evaluable patients are different classes of Adverse Effects (e.g. hepatotoxicity and myelosuppression), expansion of the cohort to 12 patients will be considered if all of the following conditions are met:
 - One of the DLTs does not appear to be dose-related
 - The Adverse Effects are readily reversible
 - The study chair, DVL statistician, DVL committee chair or vice chair, and IND sponsor all agree that expansion of the cohort is acceptable

If fewer than 1/3 of patients in the expanded cohort experience dose-limiting toxicities, the dose escalation can proceed.

THIS PROTOCOL IS FOR RESEARCH PURPOSES ONLY, SEE PAGE 1 FOR USAGE POLICY

- The DLTs observed in the pharmacokinetic (PK) expansion cohort will be counted towards the total number of DLTs observed at the MTD during the dose escalation portion of the study. If $\geq 1/3$ of the cohort of patients at the MTD (during the dose escalation plus the PK expansion) experience DLT then the MTD will be exceeded.

11.2.3 Recommended Phase 2 Dose (RP2D):

After accrual to dose level 2 is completed, PK comparisons from dose levels 1 and 2 will be performed. An expansion cohort will accrue at the lowest tolerable dose at which C_{min} of ≥ 50 μ g/mL has been achieved in at least 5 out of 6 evaluable patients to acquire PK data in a representative number of young patients (i.e. patients < 12 years old). If at least 10 out of the total 12 evaluable patients have a steady state concentration of ramucirumab greater than 50 μ g/mL, then the RP2D has been defined. If $C_{min,ss}$ of ≥ 50 μ g/mL has not been achieved in at least 5 out of 6 evaluable patients from dose level 2, and if the MTD has not yet been reached, then dose level 3 will be considered.

11.3 **Dose Escalation and Determination of MTD**

The rolling six phase 1 trial design will be used for the conduct of this study.⁸² Two to six patients can be concurrently enrolled onto a dose level, dependent upon (1) the number of patients enrolled at the current dose level, (2) the number of patients who have experienced DLT at the current dose level, and (3) the number of patients entered but with tolerability data pending at the current dose level. Accrual is suspended when a cohort of six has enrolled or when the study endpoints have been met.

Dose level assignment is based on the number of participants currently enrolled in the cohort, the number of DLTs observed, and the number of participants at risk for developing a DLT (i.e., participants enrolled but who are not yet assessable for toxicity). For example, when three participants are enrolled onto a dose cohort, if toxicity data is available for all three when the fourth participant entered and there are no DLTs, the dose is escalated and the fourth participant is enrolled to the subsequent dose level. If data is not yet available for one or more of the first three participants and no DLT has been observed, or if one DLT has been observed, the new participant is entered at the same dose level. Lastly, if two or more DLTs have been observed, the dose level is de-escalated. This process is repeated for participants five and six. In place of suspending accrual after every three participants, accrual is only suspended when a cohort of six is filled. When participants are inevaluable for toxicity, they are replaced with the next available participant if escalation or de-escalation rules have not been fulfilled at the time the next available participant is enrolled onto the study.

The following table provides the decision rules for enrolling a patient at (i) the current dose level (ii) at an escalated dose level, (iii) at a de-escalated dose level, or whether the study is suspended to accrual:

# Pts Enrolled	# Pts with DLT	# Pts without DLT	# Pts with Data Pending	Decision
2	0 or 1	0, 1 or 2	0, 1 or 2	Same dose level
2	2	0	0	De-escalate*

3	0	0, 1 or 2	1, 2 or 3	Same dose level
3	1	0, 1 or 2	0, 1 or 2	Same dose level
3	0	3	0	Escalate ^{**}
3	≥ 2	0 or 1	0 or 1	De-escalate [*]
4	0	0, 1, 2 or 3	1, 2, 3 or 4	Same dose level
4	1	0, 1, 2 or 3	0, 1, 2 or 3	Same dose level
4	0	4	0	Escalate ^{**}
4	≥ 2	0, 1 or 2	0, 1 or 2	De-escalate [*]
5	0	0, 1, 2, 3 or 4	1, 2, 3, 4 or 5	Same dose level
5	1	0, 1, 2, 3 or 4	0, 1, 2, 3 or 4	Same dose level
5	0	5	0	Escalate ^{**}
5	≥ 2	0, 1, 2 or 3	0, 1, 2 or 3	De-escalate [*]
6	0	0, 1, 2, 3, or 4	2, 3, 4, 5 or 6	Suspend
6	1	0, 1, 2, 3 or 4	0, 1, 2, 3 or 4	Suspend
6	0 or 1	5 or 6	0 or 1	Escalate ^{**}
6	≥ 2	0, 1, 2, 3 or 4	0, 1, 2, 3 or 4	De-escalate [*]

^{*}If six patients already entered at next lower dose level, the MTD has been defined.

^{**}If final dose level has been reached, the recommended dose has been reached.

If two or more of a cohort of up to six patients experience DLT at a given dose level, then the MTD has been exceeded and dose escalation will be stopped (see [Section 11.2.2](#) for exception to rule). If there are no further dose escalations based on toxicity assessment, then the Recommended Phase 2 Dose (RP2D) will be confirmed as per [Section 11.2.3](#).

In addition to determination of the MTD or RP2D, a descriptive summary of all toxicities will be reported.

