Based on the safety profile in adults and the lack of DLTs at 8 mg/kg IV q 2 week dose level, we propose a dose finding study that, in the absence of DLTs, the recommended dose of ramucirumab in children and adolescents will be based on achieving a C_{min,ss} \geq 50 μ g/mL after 3 doses of ramucirumab administered every 2 weeks (C_{min} will be obtained course 1 day 42 \pm 2 days, *ie* 2 weeks after dose 3 and just before dose 4). A rolling 6 design will be used. Starting dose will be 8 mg/kg IV every 2 weeks x 3 doses per 42 day course. In this pediatric trial in the absence of dose limiting toxicity that defines a maximum tolerated dose, we propose a dose escalation to achieve a C_{min,ss} of 50 μ g/mL in children and adolescents with relapsed or refractory solid tumors. One observation from the RAINBOW and REGARD trials was a tendency for concentrations to be decreased in the lower body weight quartiles in population PK analysis. The planned dose escalation in children and adolescents will permit evaluation of a higher dose to achieve comparable serum exposures seen in adults [personal communication with Eli Lilly]. If the MTD is not exceeded (0 or 1 DLT/6 fully evaluable patients) at 8 mg/kg dose level, a second dose level will be explored at the escalated dose of 12 mg/kg IV q 2 weeks x 3 doses per course. After accrual to Dose Level 2 is completed, PK comparisons from dose levels 1 and 2 will be performed. If PK analysis indicates that more than one patient treated at 12 mg/kg dose level has a day 42 C_{min} significantly less than 50 μ g/mL, and the MTD has not been exceeded, additional dose levels will be considered. The next dose level will be established based on C_{min} from children who received 8 mg/kg/dose and 12 mg/kg/dose on this trial, and will not exceed 16 mg/kg per dose q 2 weeks x 3 doses (*adult MTD: 13 mg/kg weekly*). If the MTD in children and adolescents is exceeded at 8 mg/kg IV q 2 weeks x 3 doses within the 42 day evaluation period for toxicity during course 1, de-escalation to 6 mg/kg will be considered, and the recommended dose will be based on the MTD. An expansion cohort will accrue at the lowest tolerable dose at which C_{min} of \geq 50 μ g/mL has been achieved in at least 5 out of 6 evaluable patients, to acquire PK data in a representative number of young patients (*i.e.* patients $<$ 12 years old). If at least 10 out of the total 12 evaluable patients have a steady state concentration of ramucirumab greater than 50 μ g/mL, then the RP2D has been defined.

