### 5.3. Method of Assignment to Dose Level

In the rolling 6 study design, 2 to 6 patients can be concurrently enrolled onto a dose level, based on the number of patients currently enrolled in the cohort, the number of DLTs observed, and the number of patients at risk for developing a DLT. Accrual is suspended when a cohort of 6 has enrolled or when the study endpoints have been met.

**Table JVDA.1** provides the decision rules for enrolling a patient at (i) the current dose level (ii) at an escalated dose level, (iii) at a de-escalated dose level, or whether the study is suspended to accrual. For example, when 3 patients are enrolled onto a dose cohort, if toxicity data is available for all 3 when the fourth patient entered and there are no DLTs, the dose is escalated and the fourth patient is enrolled to the subsequent dose level. If data is not yet available for 1 or more of the first 3 patients and no DLT has been observed, or if one DLT has been observed, the new patient is entered at the same dose level. Lastly, if 2 or more DLTs have been observed, the dose level is de-escalated. If the dose for the fourth patient is escalated, another patient will be enrolled in the subsequent dose level and restart the decision rules for the new dose level.

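### The escalation rule can close 8 mg/kg at 3 to 5 patients, leaving the 5-of-6 trough criterion behind the RP2D undetermined at that dose

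*Protocol*

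**What the plan says.** Two descriptions of when a dose level may be left stand in the current text.

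- Protocol 2.5 makes the move to 12 mg/kg conditional: "If the MTD is not exceeded (0 or 1 DLT/6 fully evaluable patients) at 8 mg/kg dose level". SAP 5.1 uses the same words.
- Protocol 11.3 works with three patients: once all three have been assessed without a DLT, "the dose is escalated and the fourth participant is enrolled to the subsequent dose level". SAP 5.3 agrees ("the dose is escalated and the fourth patient is enrolled to the subsequent dose level"). The tables in both documents also escalate at four of four and five of five. Protocol 11.1 and SAP 5.2 ask for only two evaluable patients per level.

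The RP2D rule (Protocol 2.5, 5.3.1 and 11.2.3; SAP 5.1) is a PK rule with a fixed denominator. After level 2 has accrued, "PK comparisons from dose levels 1 and 2 will be performed". Then: "An expansion cohort will accrue at the lowest tolerable dose at which" a Cmin of at least 50 µg/mL "has been achieved in at least 5 out of 6 evaluable patients to acquire PK data in a representative number of young patients".

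Protocol 5.1 and 5.3.1 record that escalation is complete and that the RP2D is 12 mg/kg. They give neither the number treated at 8 mg/kg nor their trough results.

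**The concern.** The rolling-six table decides on toxicity, and for toxicity alone early escalation is a normal feature. This trial adds a second decision, on trough concentration, that presumes six patients at the level. Following the table can leave 8 mg/kg with three or four patients, too few to reach five successes.

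No passage sends later patients back to level 1 for PK. The table footnote bears on six at the lower level only when the higher level de-escalates, and the expansion cohort opens only at a dose already chosen. The gap therefore matters in the case where 12 mg/kg is tolerated.

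At stake is one statement: that 12 mg/kg is the lowest tolerable dose meeting the PK target. It requires that 8 mg/kg did not meet the target, which differs from 8 mg/kg not having been tested far enough to tell. Estimating the MTD and/or RP2D is a primary objective, and Part B is treated at the resulting dose.

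**Working it through.** **The plan's own size.** Three levels × 6 + 6 expansion = 24 evaluable, and 24 × 1.2 = 28.8, giving the stated 29 enrolled. The worst case is 3 × 12 + 6 = 42, and 42 × 1.2 = 50.4, giving the stated 51. Both figures reproduce. The arithmetic budgets six per level, as does the reference in Protocol 4.1.7.1 to cohorts of six. The decision table does not guarantee six.

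**When 5 of 6 is decided with n < 6.** It has failed once two patients miss, whoever would have come next. It is met once five succeed.

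- n = 3 or 4: failed with at least 2 misses, otherwise undetermined; it can never be met.
- n = 5: met at 5/5, failed with at least 2 misses, undetermined at 4/5.

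**Chance of early closure.** Inputs: 1 to 2 patients a month (Protocol 11.1) and a 42-day cycle as DLT window (5.1, 5.5). Assumptions: Poisson accrual, no DLT, no data lag, all patients evaluable. The chance that no patient arrives during one window is q = exp(−rate × 42/30.44), which is 0.252 at 1 a month and 0.063 at 2 a month. Closure at n = 3, 4, 5 has probability q, (1−q)q, (1−q)²q, and closure below six is 1 − (1−q)³ = 0.58 or 0.18 (0.33 at 1.5 a month). Simulation agrees. With a 10% DLT rate it gives about 39% and 12%. With 14 days of data lag and no DLT, the formula gives about 40% and 7%.

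**Chance that a child reaches target at 8 mg/kg.** Assumption: the adult troughs before dose 4 in Protocol 2.3.5 apply and are lognormal, with σ = √ln(1 + CV²).

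- REGARD: geometric mean 49.5, CV 81%, σ = 0.710, p = 1 − Φ(ln(50/49.5)/0.710) = 0.49.
- RAINBOW: geometric mean 45.0, CV 50%, σ = 0.472, p = 1 − Φ(ln(50/45)/0.472) = 0.41.

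As a high case, p = 0.90 is also shown.

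**Undetermined given closure at n.** For n = 3 or 4: pⁿ + n pⁿ⁻¹(1−p). For n = 5: 5p⁴(1−p).

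| n at closure | P(close at n), 1/month | P(close at n), 2/month | undetermined, p = 0.41 | p = 0.49 | p = 0.90 |
|---|---|---|---|---|---|
| 3 | 0.252 | 0.063 | 0.366 | 0.485 | 0.972 |
| 4 | 0.188 | 0.059 | 0.191 | 0.298 | 0.948 |
| 5 | 0.141 | 0.056 | 0.083 | 0.147 | 0.328 |

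**Early closure and undetermined (sum of products).**

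- 1/month, p = 0.41: 0.252 × 0.366 + 0.188 × 0.191 + 0.141 × 0.083 = 0.14.
- 1/month, p = 0.49: 0.122 + 0.056 + 0.021 = 0.20.
- 1/month, p = 0.90: 0.245 + 0.178 + 0.046 = 0.47.
- 2/month: 0.04, 0.06 and 0.14 for the same three values of p.

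**What the planned outputs would show.** Protocol 11.6.5 summarises concentrations by dose level and time, but its minimum parameter list is Cmax, tmax and AUC. SAP 6.6 assigns PK work to a sponsor group and specifies no trough analysis. The PK population (Protocol 11.6.3, SAP 6) needs one derivable parameter, not a day-42 trough. Evaluability for Cmin is not defined.

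**The case against.** The strongest reply is that the governing rule is identifiable. Protocol 2.5 itself names a rolling-six design, SAP 5.1 points to the decision rules that follow it, and the minimum is two patients per level. The six-patient parenthesis then reads as shorthand for a full cohort. That is a fair reading of intent. It lessens the conflict over escalation but not the PK gap, because it is the table that permits closure at three.

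A second reply is that small levels are often informative. This stands: a reader might infer that the criterion cannot be evaluated below six, or that the RP2D holds only if six patients had troughs at 8 mg/kg. Neither follows. One of three at target is a definite failure and would support moving on, and five of five is a definite pass. Under adult troughs, even a full cohort of six would meet the rule with probability only 0.10 (p = 0.49) or 0.05 (p = 0.41).

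A third is that a wide interval says little about cohort size in a count rule with descriptive analyses. This also stands: 3/3 has an exact 95% interval of 29–100%, and the plan's own passing result of 5/6 has 36–100%. The interval is worth reporting, but it is not the argument.

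Finally, escalation is over and concentrations will be tabulated by dose level, so part of the reporting is already planned. What is missing is the count at target and its denominator.

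**Conclusion.** The point holds as a mismatch between two decision rules, with a limited consequence for what may be claimed about the RP2D. A level closed at 3 or 4 patients cannot be shown to meet the criterion, and one closed at 5 meets it only at 5/5.

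The 58% to 18% range is the chance of early closure. It should not be read as the chance that the PK question was left open, which is about 14–20% or 4–6% under adult troughs and up to about 47% or 14% if 90% of children reach target. These figures rest on Poisson accrual, no DLT, no data lag and full evaluability. The stated 20% inevaluable rate is not modelled. DLTs or data lag make early closure less likely.

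A reader might also infer that 8 mg/kg was passed over untested, that 12 mg/kg is wrong, or that the sample size is wrong. The documents support none of these: the number treated at 8 mg/kg and their troughs are not given, and 24, 29 and 51 reproduce.

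**What to change.** Reconcile Protocol 2.5 and SAP 5.1 with Protocol 11.3 and SAP 5.3 on cohort size. Which rule applies is for the study team to state.

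In the SAP, define an evaluable day-42 Cmin and add one table by dose level:

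- number treated;
- number with an evaluable day-42 Cmin;
- x/n at or above 50 µg/mL, with exact 95% CI;
- status of the 5-of-6 criterion: met, failed (at least two misses) or undetermined.

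Describe 12 mg/kg as the lowest tolerable dose meeting the PK target only if 8 mg/kg is classified as failed. If it is undetermined, say so. The cost is wording and one table from samples already scheduled, with no new patients.
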